- c. Subjects with the highest pulmonary arterial pressures will have the greatest restoration of right heart function with sildenafil treatment.

Click here to enter text.

C. Methods, Materials and Analysis

This study will be performed over summers 2019 and 2022 in Split Croatia and the Cardiopulmonary and Respiratory Physiology lab at the University of Oregon in Eugene, Oregon for research activities involving breath hold diving and SCUBA diving subjects. We will perform research activities in breath hold divers and age and sex-matched breath hold diver controls while in Split Croatia. In Eugene, OR we will only perform research activities in age, PFO, and sex-matched breath hold diver controls. SCUBA diving studies will only be performed in Croatia. My lab has extensive experience examining IPAVAL and PFO blood flow as well as measuring pulmonary artery pressure under various environmental challenges such as during exercise, pre- and post-diving and high altitude. We will use saline contrast echocardiography to detect and differentiate between blood flow through IPAVAL and PFO, as we have many times before. We will use Doppler ultrasound as before to quantify differences in pulmonary artery pressure with and without the use of sildenafil. We will use the Journal of American Society for Echocardiography recommendations for making right and left heart function measures as before. We will collaborate with Professor [name], MD, PhD who has extensive experience working with professional, elite, world-record level, breath-hold divers and SCUBA divers. He also has the required laboratory space and resources for performing these experiments at the University of Split Medical School, Split Croatia. There are many elite breath-hold divers that live in Croatia and [name] has established an excellent rapport with the divers and their coach [name] who is with the Faculty of Kinesiology at the University of Zagreb, Croatia. Additionally, [name] has also established an excellent rapport with the Croatian Military for the SCUBA diving studies to be performed using highly experienced divers on a Croatian Navy Base field site that has the required laboratory space and resources for performing the proposed studies. [name] has significant experience working with these groups so it will prevent the possibility of any cultural or political issues interfering with this work. Additionally, [name] and I have worked together before on several projects, see [name] CV for verification as needed.

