
Briefly we will use a single-blind, placebo-controlled study to determine the impact of sildenafil (50 mg, oral) on IPAVAL and PFO blood flow and right heart function and pulmonary pressures. We will use 40 breath-hold divers (20 PFO+, 20 female), 40 age-matched (within 5 years) breath-hold diver Controls (20 PFO+, 20 female), and 50 (25 PFO+, 25 female) SCUBA divers. Sildenafil will be given before the breath hold in the breath-hold divers but after SCUBA diving to avoid any potential decompression illness complications.

Screening at each study visit: All subjects with child bearing potential will be required to take a urine pregnancy test before each visit begins. A positive test at any time will result in exclusion.

Breath Hold Diving Subjects & Controls (Objectives 1 - 3)

Visit 1 Overview: Subject consent, screening, lung function and anthropometrics. Subjects will ingest either a placebo or sildenafil (50mg, oral), wait an hour for peak effect and then breathe low oxygen and high CO2 gas mixtures that mimic blood gases during a breath hold, during which ultrasound measures of the heart and lungs will be made (~4.5 hrs). Note: Breath hold subjects will breathe lower oxygen concentrations and higher carbon dioxide levels than control subjects but slopes of these responses will still be comparable.

Visit 1 Details:

Subjects will undergo informed consent, fill out a health history questionnaire (~45 min).

Subjects will be comprehensively screened for any cardiac abnormalities. Amount of blood flow travelling through the PFO and IPAVAL will be graded using saline contrast echocardiography while the subject is breathing

room air (PFO and IPAVA blood flow) and breathing 100% O₂ (PFO blood flow only). Pulmonary artery pressure will also be measured using ultrasound. Subjects will undergo an intravenous blood draw. We will take 21 mL (~2 Tablespoons) of IV blood (~1.25 hrs)

Subjects will perform pulmonary function testing. (15min)

The subjects will be instrumented with forehead oxygen saturation monitor, ECG and blood pressure cuffs and baseline ultrasound measures of cardiac output, pulmonary pressure and left and right heart function measures will be made before breath hold (~30 min)

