- **Intravenous Catheter (IV) and blood draw** (Days 1 & 2 for Breath Hold and SCUBA divers): We will place a 20-22 gauge (small diameter) IV into a vein in the subject's arm that will be used for the rapid injection of the agitated sterile saline for TTSCE. This catheter will also be used to measure serum inflammatory mediators. Blood will be centrifuged and de-identified serum stored at -80°C until assayed by ELISA kit. For the breath hold dive arms, blood will be drawn once on the first visit pre-breath hold (21 mL). For the SCUBA arm, blood will be drawn pre- and post-dive for both visits (21 mL per blood draw x4 blood draws). Total IV blood draw is therefore approximately 84 mL for SCUBA subjects.

- **Breathing low oxygen and high carbon dioxide** (hypercapnic hypoxia) to mimic breath hold (Days 1 & 2, breath hold and breath hold control subjects only):

Subjects will take either sildenafil or a placebo, and will be instrumented during the ~1 hour wait till peak effect. After being instrumented with ECG, forehead saturation and blood pressure monitoring equipment, subjects will breathe room air for 5-10 minutes to measure baseline breathing. During the first 5 minutes of the hypercapnic hypoxic conditions, subjects will breathe room air through a 2-way non-rebreathing Hans Rudolph mouthpiece. During the resting period end tidal (expired) Oxygen will be clamped at 100 mm Hg, while end tidal (expired) carbon dioxide will be maintained at resting levels (~30-40 mm Hg). Upon completion of the baseline measurements, end tidal carbon dioxide will be increased while end tidal oxygen will be reduced.

The values for oxygen and carbon dioxide for breath hold divers will be changed to 45-50 mm Hg CO2 and 50-60 mm Hg O2 and held at this level for approximately 5 minutes while ultrasound measures are made, then subsequently changed to 55-60 mm Hg CO2 and 30-40 mm Hg O2 and held at this level for approximately 5 minutes, while ultrasound measures are made. These values of oxygen and carbon dioxide were chosen based on previous values published in breath hold divers by my collaborating investigator [name] (Willie et al., J Cereb Blood Flow & Metab 2015).

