
Men and women aged 18-65 recruited from patients in the surrounding Split Croatia community who are elite breath hold divers and highly experienced SCUBA divers, and or age, sex and PFO-matched controls from the surrounding Split Croatia area and the surrounding Eugene/Springfield area for breath hold dive studies only.
	
Previous history of coronary artery disease (ischemic heart disease such as angina, heart attack, myocardial infarction). Currently taking medications or herbal supplements for any heart or respiratory disease that they cannot stop taking for 48hrs prior to testing (seasonal allergy medication not included in exclusion medications). Anyone who is pregnant or trying to become pregnant. Individuals taking Sildenafil or products similar to Sildenafil, such as Tadalafil (Cialis) and Vardenafil (Levitra/Staxyn). Individuals taking NITRATES and other Nitric Oxide donors. If subjects can refrain from using PDE-5 inhibitors for 48 hours before each study day then they will be allowed to participate.
 
Previous history of any condition that would prevent the subject from breathing low oxygen and high carbon dioxide mixtures that mimic a breath hold. (breath hold diving subjects only).
 
Previous history of any condition that would prevent the subject from performing a SCUBA dive. (SCUBA diving subjects only).
 
Control breath-hold dive subjects can't have previous breath hold diving experience
 
Subjects will be excluded from telemetric pill ONLY if they have a history of obstructive diseases of the gastrointestinal tract including diverticulosis, diverticulitis, inflammatory bowel disease, peptic ulcer disease, Crohn's disease, ulcerative colitis, or previous GI surgery.

2. Detailed Recruitment information:

Breath hold divers, controls and experienced SCUBA divers will be recruited using existing contact information by our collaborators in Split. Some control subjects for the breath-hold arm of the study (NOT SCUBA DIVING arm) will be recruited from the Eugene/Springfield area. Additionally, subjects will be provided information about the opportunity to participate in this research by word of mouth and announcements by coaches and affiliated diving personnel associated with this select group of individuals. Breath-hold control subjects will be informally recruited by word of mouth and announcements by coaches

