as well, but they will be excluded if they have previous experience with breath-hold diving. In Eugene, breath-hold control subjects will be recruited by recontact from previous studies, word of mouth, and announcements by coaches, but they will be excluded if they have previous experience with breath-hold diving. Breath hold divers will be asked if they have anyone in mind that might be interested in breath-hold diving that have no previous experience doing it before, thus, helping us collect a control group.

While word of mouth and preliminary information about the study will be distributed by coaches and others in the diving community, formal recruitment will be conducted upon individuals contacting the research team. The research team will review the details of the experiment and the inclusion/exclusion criteria with each subject to allow them to make a decision regarding participation independent of peer influence. Our collaborators in Split are fluent in both Croatian and English, and will be able to explain all study procedures, data handling, and consent process in Croatian for those subjects who are not fluent in English. Control subjects from the Eugene/Springfield area will use English versions of the consent form.

3. Screening at each study visit: All subjects with child bearing potential will be required to take a urine pregnancy test before each visit begins. A positive test at any time will result in exclusion. Prior to the first visit each participant will be questioned regarding health history and current medications. Participants will be excluded if they meet any of the exclusion criteria listed in Table 1. For inclusion in core temperature measurements, subjects will be screened for the history of obstructive GI disorders during the consent meeting, during which they will be asked if they have an history of any of the GI disorders/diseases (including diverticulosis, diverticulitis, inflammatory bowerl disease, peptic ulcer disease, Crohn's disease, ulcerative colitis, previous GI surgery). This will be addressed when going through the exclusion criteria with subjects.

4. Compensation:

Subject Compensation (maximum of \$50 for US subjects or 330 Croatian Khuna (HRK)) for either the breath hold diving and SCUBA studies in Croatia):

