- **Visit #1 (Breath Hold, Breath Hold Control and SCUBA Subjects): \$30.00 for US subjects or 220 Croatian Khuna for Croatian subjects (HRK):** Completing the informed consent and health history questionnaire and echocardiographic screening and blood draw will pay \$5.00. The pulmonary function tests will pay \$5.00. Subjects who choose not to participate upon review of the informed consent or are excluded based on any findings during this visit will be paid for their degree of visit completion, that is \$5.00 if the subject decides not to participate after reviewing the informed consent; \$ 10.00 for participation in the screening procedures; total compensation for reviewing the informed consent and participating in screening is \$10.00. Subjects will be paid \$20 for either breathing low oxygen and high carbon dioxide or for performing the SCUBA dive. Compensation will be converted from USD to local currency upon arrival to Croatia. Estimates for payments are listed here based on current rates of exchange.
- **Visit #2 (Breath Hold, Breath Hold Control and SCUBA Subjects): \$20.00 for US subjects or 110 Croatian Khuna (HRK):** Subjects will be paid \$20 for either breathing low oxygen and high carbon dioxide or for performing the SCUBA dive.

Any subject that withdraws (or is withdrawn) before the end of the study will receive prorated payment up to the point of completion.

E. Informed Consent Process

The Informed Consent document provided to subjects will be posted to the regulations.gov website in compliance with OHRP guidelines and 45 CFR 46.116(h).

Informed consent will be administered to each subject by the primary investigator and colleagues. For potential subjects who are only fluent in Croatian and not English, a native Croatian speaker from [name] lab will perform the informed consent process. The Informed Consent document provided to subjects will be posted to the regulations.gov website in compliance with OHRP guidelines and 45 CFR 46.116(h). English consent forms and English consent will be used for subjects in the US.

The primary investigator is well versed in the process of informed consent and has trained his co-investigators thoroughly on how to best perform this procedure. The PI will ensure that all investigators obtaining consent have experience in the informed consent procedure and are capable of adequately discussing the related physiology, study procedure and potential risks.

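### Table 1's exclusion for people who cannot safely breathe the study gas carries a label that, read literally, omits the up to 40 breath-hold controls who also breathe it

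*Combined protocol and SAP*

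**What the plan says.** Table 1 in section D has one exclusion that concerns tolerance of the gas. It covers a history of any condition that would prevent "breathing low oxygen and high carbon dioxide mixtures that mimic a breath hold. (breath hold diving subjects only"). The next line is a parallel exclusion for conditions that prevent a SCUBA dive, limited to the SCUBA subjects.

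Section D, item 3 (Screening at each study visit) makes the table operative: "Participants will be excluded if they meet any of the exclusion criteria listed in Table 1".

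The gas procedure in section C is headed "hypercapnic hypoxia) to mimic breath hold (Days 1 & 2, breath hold and breath hold control subjects only"). Section A, Objective #3, also has controls go through the procedures of Objectives #1 and #2. Section C plans 40 controls, and section D, item 1 gives the same ceiling as up to 20 men and up to 20 women.

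On sites, section C states: "In Eugene, OR we will only perform research activities in age, PFO, and sex-matched breath hold diver controls".

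**The concern.** The people who receive the exposure and the people the exclusion names may not be the same. If a screener takes the label at its word, the only criterion about tolerating the gas is never asked of a control. At Eugene, where only controls are tested, it would apply to nobody.

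The other Table 1 lines do not fully replace it. The medication line excludes only those who cannot pause a heart or respiratory drug for 48 hours. A control whose respiratory condition is untreated, or whose drug can be paused, passes that line. Spirometry is done at Visit 1, but no result is named as a reason to exclude.

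What is at stake is participant safety. Sample size, error rates and the comparisons the study makes are not affected.

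**Working it through.** **1. Who breathes the gas.** Controls: 20 men + 20 women = 40, which agrees with the 40 in section C. Divers: 40. Together 40 + 40 = 80 people have the gas procedure. With 50 SCUBA divers the total is 80 + 50 = 130, the plan's own grand total.

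**2. How the exposures compare (section C, end-tidal targets in mm Hg).**

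| Step | Divers CO2 | Controls CO2 | Divers O2 | Controls O2 |
|---|---|---|---|---|
| 1 | 45-50 | 45-50 | 50-60 | 60-70 |
| 2 | 55-60 | 55-60 | 30-40 | 40-50 |

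CO2 difference: 0 at both steps. O2 difference: controls are 10 mm Hg higher at both steps. Time on altered gas per control: 2 steps x about 5 minutes x 2 visits = about 20 minutes.

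**3. What the label could mean.**

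*Divers only.*
- The section C heading reads "Breath Hold Diving Subjects & Controls (Objectives 1 - 3"). It uses almost the same phrase as the Table 1 label and then adds controls as a further group.
- The gas procedure's own heading, quoted above, names both groups.
- The compensation text in section D lists three groups: "Visit #2 (Breath Hold, Breath Hold Control and SCUBA Subjects").

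*Whole breath-hold arm.*
- The label is one of a pair with the SCUBA label on the next line, so the two may simply separate the arms.
- Another line in the same cell speaks of "Control breath-hold dive subjects", which makes controls a kind of breath-hold subject.
- Section C describes Split and Eugene together as places "for research activities involving breath hold diving and SCUBA diving subjects", although Eugene tests only controls.
- Under Description of Data Collection Procedures, the ultrasound screening and spirometry are labelled for breath-hold and SCUBA divers, yet the Objectives 1-3 visit schedule gives both to controls.

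No sentence in the document decides between the two.

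**4. How many people fall outside the criterion.** Divers only: up to 40 of the 80 who breathe the gas. Whole arm: 0 of 80. These figures count people whom the label does not name. They do not count people with a disqualifying condition, and the document gives nothing from which that number could be derived.

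**The case against.** The strongest reply is that the whole-arm reading is the natural one inside Table 1. The two labels sort by exposure, gas or dive. The inclusion cell places controls within the breath-hold studies, and the recruitment text in section D speaks of controls for the breath-hold arm. A divers-only rule would also be odd, since it would test tolerance in elite breath-hold divers and skip people with no such experience. If every arm label were read that strictly, controls would drop out of the ultrasound screening and spirometry too, which is plainly not intended.

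Much of this stands. It makes the whole-arm reading plausible, perhaps likelier. It does not remove the ambiguity, because elsewhere the protocol does name controls separately, including in the heading of the gas procedure itself. Two careful screeners could apply the line differently.

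The reply is also right about size. Section G calls the severity of the gas risks potentially high. It then says that, with brief exposure and careful monitoring, a serious event is very unlikely. Controls keep the health history, cardiac screening, the unrestricted Table 1 exclusions, and ECG and saturation monitoring. The compensation text shows that subjects can be excluded on Visit 1 findings.

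A reader might infer that controls go to the gas unscreened, or that the sponsor chose to exempt them. The documents support neither. The screens just listed apply to controls, and the intent behind the label is not stated.

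**Conclusion.** The point holds as a minor safety correction to ambiguous wording. The label leaves out up to 40 controls on the literal reading and none on the whole-arm reading, and the documents do not settle which was meant. The practical gap is small under either reading, and the number of controls at risk is unknown. It would be tempting to attach a probability that at least one unsuitable control is exposed. That would need the share of controls who have such a condition and pass every other screen. The documents give no such share, so no probability is offered.

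The conclusion rests on two things: that Table 1 is applied as written, as section D, item 3 says, and that controls receive the gas as section C schedules it.

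**What to change.** In Table 1, change the bracketed label on the gas-tolerance exclusion to: *breath hold diving and breath hold control subjects*. This matches the two groups named in the heading of the gas procedure in section C. If the whole arm was always meant, the change only states that intent. If not, it closes the gap.

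The cost is one label, with no new procedure, visit or change to the sample size. The downside is that a control with such a condition is screened out and may need to be replaced. The benefit is limited by timing: the document is dated Sept 7, 2022, and section C places the work in the summers of 2019 and 2022, so only controls not yet tested would gain.
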